2-3 weeks after parent/caregiver and child actigraphs are returned and analyzed by a member of the team, a phone meeting will be scheduled at a convenient time for the participants. A member of the team will provide written and verbal feedback to the child and their parent about their sleep. Based on this assessment, one of three web-based modules will be assigned.

Table 2. SLEEPSMART Modules

Module	Goals	Strategies
Bedtime routine	Structured, consistent bedtime routine \leq 30 minutes in length and implemented consistently	Family develops tailored routine, uses bedtime chart to maintain routine, problem-solving around barriers to routine
Sleep Quality	Sleep scheduling to allow for 9-11 hours of nighttime sleep (child) or 7-9 hours (parent); sleep onset-falls asleep within 30 minutes, minimal nighttime awakenings.	Family sets sleep/wake schedule that allows for enough sleep; strategies for decreasing sleep disruptions/awakenings; problem-solving around barriers to routine.
Sleep Environment	Creating sleep environment conducive to sleep – minimize noise, light, media exposure.	Family develops quiet, dark sleep environment, decreases nighttime media; problem-solving around barriers to routine.

A member of the team will instruct the family on how to access the SLEEPSMART website and their assigned module. Children will be instructed to log on once per week to the website to complete a module and assignment, designed to take about 30 minutes to complete. The SLEEPSMART assigned modules will begin with an educational module, then direct participants through goal setting, anticipated barriers, and problem solving. Web pages will include fillable responses to queries, instructions, and assignments. Tasks for children will use multimedia elements to enhance delivery of information, such as links to videos and pictures targeting self-efficacy, motivation, and patient activation. The materials used will be modified from an existing intervention, Sleep Habits in Preschoolers (SHIP), which has been pilot tested and has enrolled 450 typical developing preschool children and their parents (PI: [name]).

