Submissions and progress will be monitored by a member of the research team, who will send email, call or text with reminders (whichever the family prefers) and answer questions as needed, review progress, and help problem solve any technology issues or barriers to implementing skills. This online structure and feedback process is modeled after the work by [name], Co-I on this grant, who has successfully implemented web-based interventions with parents and children.

T2 – IMMEDIATELY FOLLOWING INTERVENTION ASSESSMENT

At the end of the 6-week SLEEPSMART intervention, for both the treatment and control groups will be mailed actiwatches, and parents and children will wear for 10 days. They will also complete the daily sleep

diary as described before. Actigraphs and sleep diaries will be returned via prepaid envelopes. Plus the above questionnaires in Table 2.

T3 – 1 MONTH following baseline

For both the treatment and control groups, activewatches will be mailed to parent/child participants to wear for 10 days. They will also complete the daily sleep diary as described before. Actigraphs and sleep diaries will be returned via prepaid envelopes. Parents and children will individually complete the instruments/research items below, nearly identical to T0 baseline visit with the exception of removing the demographic questionnaire, and use of health care utilization survey (exit) for parents and the SLEEPSMART Acceptability Questionnaire. The parent/caregiver will be given a link with the electronic instruments preloaded and instructed to complete the instruments to the best of their ability. If questions arise, a member of the research team will answer as needed. After completing the below listed activities, parent and child participants will interviewed together using semi-structured interview questions to assess participant acceptability of the SLEEPSMART Study.

--	--	--	--

5.2 Data variables. Describe the specific data you will obtain (including a description of the most sensitive items). If you would prefer, you may upload a list of the data variables to the **Supporting Documents** SmartForm instead of describing the variables below.

Screening

Parent report of yes to either of the following questions: “does your child has difficulty with sleep quality and/or does poor sleep impact your child’s day-to-day function (school, interacting with peers, hobbies)?” **Pediatric Sleep Questionnaire (PSQ) Sleep Related Breathing Disordered Scale**

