Power. We will enroll 60 dyads for a projected sample size of 50 (25/group), assuming 15% attrition. This meets recommendations for pilot trials⁷³ and provides 80-90% power to detect moderate effects based on a RM ANOVA model with three repeated measures and a correlation of 0.3 between the measurements. This power calculation was based on the moderate to large effect sizes for our outcomes of interest (total sleep time, $d=.48$; health related quality of life, $d=.51$; and fatigue, $d = .79$) found in our previous research.

Intervention. All JIA children and parents will receive access to the SMID program, which consists of two separate, password-protected web programs, one for child access and one for parent access. The intervention is completed in an 8-week period. The program design and treatment content of SMID follow cognitive behavioral, social learning, and family systems frameworks. Given the important role of parents in children's self-management of sleep deficiency, parents are engaged throughout the intervention period in their own treatment content intended to support their child's goals and to learn strategies to modify their own behavior in response to their child's sleep deficiency. The child modules will include: sleep education, sleep skills training

(e.g., daily record of activities before bed, sleep routine and schedule), lifestyle changes, relaxation techniques positive coping, relapse prevention, reward systems for activity participation. The parent modules include: sleep education, use of attention and praise to increase positive coping, strategies to support self-management skills and goals, modeling and communication. The program is designed to enhance self-management of sleep. Children set structured and personalized goals aimed at improving their self-management skills and sleep. Given the importance of

Table 2: Measures

Concept	Measure: Target and Description including Duration and Frequency of Administration
Sleep Deficiency	
Inadequate Sleep	Actigraphy continuous recording of child's sleep-wake activity using (Actiwatch-L, MiniMitter-Respironics, Bend, OR). ²⁵⁻²⁷ Derived parameters: total sleep time, sleep efficiency, sleep onset (bedtime), sleep offset (wake time), wake after sleep onset; (T1,T2,T3) Sleep Diary daily recording of child's pre-bedtime activities (media use, sports, caffeine intake), daily sleep (time to bed, sleep onset, # night awakenings); medications, & daytime activities (T1,T2,T3)

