Data Analysis Plan. Descriptive summaries of recruitment outcomes (number of contacts made related to interest in the study, numbers screened, eligible, enrolled, completed), and retention (number of parents and children who completed the study, dropouts, reasons given, timing of withdrawals) will be reported. **Treatment engagement** will be measured by completion of at least one module in the SMID program while **adherence** is defined as the completion of 5 or more modules. The administrative interface of the SMID program will have a tracking system in place for recording each time a user logs onto the web program. **Overall usage statistics** will include monitoring of program usage (number of logins, duration of time spent completing, time spent on a page or feature). Each module will contain multiple-choice quizzes concerning the content presented as well as behavioral assignments, fill-in-the-blank fields, and use of the diary tracker. All data fields that are completed within modules are stored, generating a comprehensive activity record of module specific use including self-management tasks. Exit interviews will be assessed as described above.

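### Is the adherence cut-off of five modules out of reach when each family is assigned only one?

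*Combined protocol and SAP*

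**What the plan says.** Engagement and adherence are defined once, in the Data Analysis Plan of the Research Strategy. Engagement "will be measured by completion of at least one module in the SMID program"; adherence "is defined as the completion of 5 or more modules". SMID is described in the Intervention paragraph of the Research Strategy as separate child and parent web programs covering several topics. No module count is given, and the length is stated thus: "The intervention is completed in an 8-week period".

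Section 5.1 describes the program under the name SLEEPSMART. After feedback on the baseline actigraphy: "Based on this assessment, one of three web-based modules will be assigned". The family is then shown "how to access the SLEEPSMART website and their assigned module". The pace is weekly: "Children will be instructed to log on once per week to the website to complete a module and assignment". The content is outlined as follows: "The SLEEPSMART assigned modules will begin with an educational module", and goal setting, barriers and problem solving come after it. The T2 assessment is timed thus: "At the end of the 6-week SLEEPSMART intervention". Section 5.1 does not repeat or adapt the engagement and adherence rules.

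**The concern.** The cut-off was written under one program description and the procedures give another. If a module is one of the three listed in the SLEEPSMART table of Section 5.1, a family is assigned one, and five cannot be reached. Adherence would be zero by construction, and the engagement rule of at least one module would mean finishing everything assigned. If a module is the weekly unit, a family that does everything scores 6. At full compliance in the 30 children planned for SLEEPSMART, the same records would give 0/30 or 30/30 adherent.

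In a pilot this could matter. Aim 2 of the Research Strategy sets out to determine levels of engagement, Section 1.5 names feasibility/acceptability among the primary outcomes, and those findings are meant to guide later work on the intervention. A counting unit left open could in principle be settled after the usage records are seen.

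**Working it through.** The plan has no calculated figure to reproduce here; the cut-off is a definition. The check is a count of what can be completed, followed by a comparison of the texts.

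**Inputs.** Cut-offs of 1 and 5 modules (Research Strategy, Data Analysis Plan). Six weeks, one log-on per week, one of three modules assigned (Section 5.1). Thirty children in the SLEEPSMART arm (Section 5.1, Aim 3).

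**Most units a family can complete as scheduled**

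| Unit counted | Maximum | Cut-off of 5 |
|---|---|---|
| Assigned module | 1 | not attainable |
| Weekly module and assignment | 6 weeks × 1 per week = 6 | attainable; 5/6 = 83% |

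**Which unit the text favours**

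1. The adherence rule counts modules completed. Section 5.1 speaks of completing a module in its weekly instruction, together with an assignment. What is assigned after baseline feedback is a topic area that the weekly work runs through.
2. The Intervention paragraph of the Research Strategy also places assignments at the end of each module. The pairing of a module with its assignment is therefore common to both program descriptions.
3. Counted by assigned module, adherence is 0% whatever the records show. An analyst would see that this cannot be intended and would not choose it to flatter the result. Only the weekly unit lets a cut-off of 5 separate families.

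**Whose completions count.** The separate child and parent programs appear in the Research Strategy. For SLEEPSMART, Section 5.1 gives the weekly log-on instruction to children, which points to the child's record.

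**Whether the units can be counted.** The comprehensive activity record in the Data Analysis Plan is described for SMID. For SLEEPSMART, Section 5.3 lists log-on date, time and duration, and Section 5.1 adds fillable responses and submissions monitored by staff. Completed weekly units can be identified from these without relying on log-ons alone.

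**What depends on the rule.** The power paragraph uses 25 per group and effect sizes for sleep, quality of life and fatigue. The efficacy analysis is intention-to-treat with GEE. Adherence appears in neither, and no per-protocol set is defined by it. The Data Analysis Plan also reports logins, time spent and module-specific activity, so a reader sees the usage behind the dichotomy.

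**The case for a change.** The strongest case is that a rule the reader has to infer has not been pre-specified. Section 5.1 uses the word module for the assigned topic, for the weekly unit and for the educational opening. The cut-off names SMID, not SLEEPSMART. The two descriptions also differ in length, and Section 5.1 itself places T2 at 8 weeks while calling the intervention a 6-week one. The plan does not say whether child, parent or both completions count, and it gives no denominator.

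The narrow core of this stands: no sentence in the documents states what one module is for the adherence summary of the 6-week program. The consequences drawn from it do not stand.

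- The 0/30 figure needs the reading that the text favours least.
- Expressing 5 as a share of the topics listed for SMID would need one topic to equal one module, which is nowhere stated, so such percentages describe no program in the plan.
- Aim 2 names engagement, not adherence, and at least one module can be met under either unit. Acceptability has its own instruments: the Treatment Evaluation Inventory, the end-of-study survey and exit interviews. No text links the five-module cut-off to the primary outcome.
- The natural denominator is the 30 dyads planned for SLEEPSMART, since only that arm receives the program.

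The mismatch in program length is a separate matter, on which this point takes no side.

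**Conclusion.** This is a gap that analysts fill sensibly. The cut-off reads as at least 5 of 6 completed weekly modules with their assignments (83%), and engagement as at least 1 of 6. A written clarification would keep both numbers and the same unit. The effect on sample size, power and the efficacy analysis is nil, no data are lost, and the one summary concerned is descriptive and reported beside the underlying usage.

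The conclusion rests on three assumptions: the program delivered is the weekly 6-week one of Section 5.1; completion is judged from submitted work and not from log-ons alone; and the child's record is the one counted, as the log-on instruction suggests. If the 8-week program were delivered instead, the rule would apply to the program it was written for, although its module total is not stated.

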Aim 2. Determine feasibility and initial efficacy of the SMID with children with JIA in a pilot RCT. We will determine study accrual and dropout rates as well as levels of patient acceptability and engagement in a pilot randomized controlled trial (RCT) comparing usual care to SMID intervention. Preliminary effect sizes of the SMID will be determined in youth receiving treatment compared to usual care on primary outcomes of actigraphy sleep duration, sleep quality, and feasibility/acceptability, and secondary outcomes of child and parent self-management (activation, motivation, self-efficacy), technology use, recommendations for innovative sleep monitoring. We hypothesize that children who receive technology-based SMID vs. those who receive Usual Care will achieve increased sleep duration and efficiency (quality), immediately post-treatment and at 3 month follow-up.

Sample. Sixty children, 9-11 years, diagnosed with JIA and one parent will be recruited from the Pediatric Rheumatology Clinic at SCH and remotely via a flyer on the JIA foundation website.

Recruitment. At SCH, the clinical research assistant (CRA) will give eligible JIA families a study information flyer; the flyer will also be posted on the WA JIA website. For both SCH and the JIA website, interested families will contact the CRA by calling a phone number on the study flyer. The CRA will describe the study and screen for participation. Interested participants will be sent a consent/assent forms by mail, with a prepaid envelope. The recruitment methods were fruitful in our prior studies. Inclusion and exclusion criteria for JIA children and parents is above. Gender/minority inclusion: Girls and boys are eligible; we expect to enroll more Caucasian girls because the heightened disease prevalence among Caucasian girls and its relatively low prevalence in other ethnic groups.^{57,58} JIA patients seen at SCH approximate the national ratio of female:male patients 4:1 and 95% Caucasian. Biologic variables: We will include sex as covariate in the statistical analysis due to the potential confounding effect on sleep.

Measures. **Table 2** shows the measurement plan for the study assessments.^{2-27,59-72}

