homework and practice to change behavior, several components (e.g., positive feedback loops) actively encourage user attention and motivation in order to promote skills acquisition and rehearsal. The intervention will be interactive and personalized with tailored feedback. Using a diary function on the web site, children track their sleep in real-time and can generate customized reports and graphs from their data. Modules will take an estimated 20 minutes to complete and will include multimedia elements to enhance learning. Participants will be asked to spend additional time practicing skills and completing assignments at the end of each module. A message center will allow each child and/or parent to ask questions as they progress in the program. The PI will review messages, provide individualized feedback through Web message center. The web site uses a multimedia-rich format (e.g., animations, videos, audio clips) to deliver content. The website is built on a responsive platform and can be viewed on multiple devices (e.g., smartphones, laptops, tablets) to increase ease and flexibility of use. All app and website content is (a) written at a grade 4th grade reading level, (b) developmentally appropriate for 9-11 year-olds, and (c) is based on a unifying theme/narrative.

Measurement Plan. Assessment will occur at (T1 baseline), immediately after intervention (T2) and repeated at 3 months post-intervention (T3) for both the SMID and usual care groups. All questionnaires will be administered using REDCap, a secure web-based tracking and on-line data acquisition system. Children will wear an actigraph a reliable and validated measure of sleep²⁵⁻²⁷ on their non-dominant wrist for 10 consecutive days, and complete an electronic symptom diary. After 10 days, parents will mail back the actiwatches in a prepaid self-addressed envelope used in PIs prior sleep studies.^{1,27,35} Actigraphy data will be downloaded, scored, and a member of the team will follow up with parents to discuss the baseline sleep patterns within 1 week. Estimated time burden is 20 minutes for children and 10 minutes for parents. Response burden is minimized by online administration, which saves and stores responses.

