Perceived usefulness and acceptance. About one third of all participants (33%; 20 out of 60 dyads) will be interviewed at study exit to assess their overall perceptions of the web-based program, the perceived usefulness and ease of use. All interviews will be conducted by trained RA in person or via telephone and will

be digitally audio-recorded. Specifically, questions will address the perceived impact of the system on sleep self-management, barriers and facilitators to use and whether children and parents would foresee future use and recommend the system to others. Audio-recordings will be transcribed and then analyzed by members of the research team. Following procedures explicated by Braun and Clarke,⁵⁶ described above.

Randomization. Following completion of baseline assessments, participants will be randomized to one of two treatment arms. Across groups, children will continue to receive their usual specialty medical care for JIA. A blocked randomization scheme will be generated using an online program to derive randomization assignment, programmed in the Internet sleep intervention, and not accessible to study investigators. Enrolled participants will be continuously randomized.

Usual Care. This treatment arm will receive usual JIA care, including annual Rheumatology clinic visits, medications, routine clinical and laboratory tests, physical therapy, follow-up appointments. Sleep intervention is not a part of usual care. The CRA will routinely review medical records and document any changes in medical care received during the intervention period.

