Data will be reviewed for completeness and errors including consistency checks for relevant variables. Tabular and graphical methods of data exploration including frequency tables and scatterplots will be used to explore distributions of study variables. We will adjust for sex, and considered use of either RM ANCOVA or generalized estimating equations (GEE) to evaluate intervention effects. We prefer GEE since it allows us to account for clustering of repeated assessments within individuals as well as the longitudinal nature of the data and provides higher power. Missing data will be examined for patterns and we will employ GEE multiple imputation to carry out ITT analysis. Single degree of freedom contrasts by group will be examined if there are significant changes in sleep measures from pre- to post-treatment and/or from pre- to 3-month follow-up for SMID vs Usual Care. Secondary treatment outcomes will be examined using GEE to explore for mean changes across time and between groups using interaction terms and contrasts. The range of outcome measures will allow us to obtain experience with alternative measures of sleep, self-management measures that will inform our future research. Outcome data will also be used to generate effect size point estimates for the future large-scale trial. **Design Considerations, Alternative Strategies and Timeline.** Project constraints on research time and resources will pose study limitations, which we have adjusted for in the study design and timeline. As the study requires participant enrollment for 5 months, we anticipate some challenges around retention, and have addressed this with a number of strategies described below. Co-I, [name] successfully recruited and retained youth with chronic pain in Web-based interventions over a period of 12 months (>90% retention). An attention control group and other parent/child variables were considered but feasibility, acceptability, and proof of concept were prioritized for this initial phase. **Rigor and Transparency** will be ensured by: 1) the proposed methods (usability, expert panel, parent/child input); 2) use of successful retention strategies from prior studies; 3) documentation of attrition; 4) sample size derived from a priori power analysis; 5) statistical methods to account missing data and change overtime. **Retention.** We will make every effort to retain participants with fruitful methods used in our prior studies including: 1) automated reminders built into the Web program; 2) phone calls scheduled at convenient times, 3) incentives for completion of each assessment (\$20 gift card/each Aim 1; Aim 2 [T1 \$40 gift card each; T2 \$60 gift card each; T3 \$80 gift card each]), 3) semi-structured interviews *prior to* intervention development; and 4) exit interviews post-intervention. **Strengths** include: 1) successful recruitment of JIA children; 2) expertise in sleep, technology-based interventions, usability assessments; 3) leveraging of successful methods in a prior Web-based interface; 4) development of the first low resource demand, convenient, and personalized sleep self-management intervention for JIA. Findings generated will address important methodological issues needed to develop innovative sleep self-management intervention for children with chronic illnesses and their parents.

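### The efficacy model does not adjust for the T1 value of the outcome; at the plan's correlation of 0.3, contrasting change from T1 carries 54% more variance than a baseline-adjusted contrast.

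*Combined protocol and SAP*

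**What the plan says.** All the relevant text is in the Research Strategy part of the combined protocol and SAP.

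- **Model and covariates (Data Analysis Plan):** "We will adjust for sex, and considered use of either RM ANCOVA or generalized estimating equations (GEE) to evaluate intervention effects". The plan then states a preference for GEE, partly because it expects higher power. The recruitment text under Aim 2 repeats the covariate: "We will include sex as covariate in the statistical analysis". No other covariate is named in either place.
- **Efficacy contrast (Data Analysis Plan):** single-degree-of-freedom contrasts by group look for "significant changes in sleep measures from pre- to post-treatment and/or from pre- to 3-month follow-up for SMID vs Usual Care". Secondary outcomes are handled by GEE with interaction terms and contrasts.
- **Role of T1 (Power; Measurement Plan):** the sample size is "based on a RM ANOVA model with three repeated measures and a correlation of 0.3 between the measurements". The Measurement Plan lists three assessments, T1, T2 and T3, so T1 is one of the three repeated measures.
- **Timing of T1 (Randomization):** "Following completion of baseline assessments, participants will be randomized to one of two treatment arms".
- **Size (Power):** "We will enroll 60 dyads for a projected sample size of 50 (25/group), assuming 15% attrition".
- **Use of the results (Data Analysis Plan):** "Outcome data will also be used to generate effect size point estimates for the future large-scale trial".

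**The concern.** A between-arm contrast of change subtracts the whole T1 value from the follow-up value, that is, it uses T1 with a coefficient fixed at 1. With equal SDs at T1 and follow-up, the best coefficient is the correlation between them. When that correlation is low, as the plan assumes, subtracting all of T1 adds more noise than it removes. Regressing follow-up on T1, or constraining the arms to one T1 mean, uses the same data with the right weight.

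Choosing GEE does not solve this. With complete data, an exchangeable GEE with group, time and group-by-time terms returns exactly the difference in mean change.

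What is at stake is the precision of the effect estimates, from about 50 completing dyads, that the definitive trial is to be planned on. Bias is not at stake, because assignment follows the T1 assessment.

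**Working it through.** **Inputs from the plan (Power):** correlation 0.3 between measurements; 60 dyads enrolled, 50 completing, 25 per arm; d = 0.48 for total sleep time; 80-90% power.

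**Assumptions:** equal SDs at T1 and follow-up, a common correlation, and two-sided alpha 0.05 (the plan states no alpha). Correlations other than 0.3 are shown only as a range.

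**1. The plan's own power figure.** Take the RM ANOVA group-by-time test with N = 50, m = 3 and f = d/2 = 0.24. Then lambda = N·m·f²/(1−rho) = 150 × 0.0576/0.7 = 12.3 on 2 and 96 df, which gives 88.2% power. With f = 0.25 it is 90.8%. The stated range therefore reproduces as an unadjusted group-by-time test, which supports reading T1 as one of the outcomes.

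**2. Variance per visit, in units of SD².**

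- Change from T1: 2(1−rho)
- Adjusted for T1: 1−rho²
- Ratio: 2(1−rho)/[(1−rho)(1+rho)] = 2/(1+rho)

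| rho | Change | T1-adjusted | Ratio |
|---|---|---|---|
| 0.3 (plan) | 1.40 | 0.91 | 1.54 |
| 0.5 | 1.00 | 0.75 | 1.33 |
| 0.6 | 0.80 | 0.64 | 1.25 |
| 0.7 | 0.60 | 0.51 | 1.18 |

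At rho 0.3 a change contrast would need about 25 × 1.54 = 38 completers per arm to match 25 per arm with adjustment.

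**3. 95% CI half-width at 25 per arm:** t × √(2 × variance/25), with 48 df for change and 47 df for adjusted.

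- rho 0.3: 2.011 × √0.1120 = 0.673 SD, against 2.012 × √0.0728 = 0.543 SD
- rho 0.5: 0.569 against 0.493 SD
- rho 0.7: 0.441 against 0.406 SD

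**4. Cost of estimating the T1 slope.** With 50 children this inflates the adjusted variance by about 1 + 1/46 = 1.022, so the ratio at rho 0.3 becomes 1.538/1.022 = 1.51 and the half-width about 0.549 SD. Simulation at 25 per arm gave ratios of 1.50, 1.31 and 1.14 at rho 0.3, 0.5 and 0.7.

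**5. Attrition.** With 30 per arm randomized, 15% lost, all available data used and the covariance taken as known, the ratio is 1.46-1.54 at rho 0.3, 1.28-1.33 at 0.5 and 1.15-1.18 at 0.7, depending on when dropout occurs. A simulated exchangeable GEE (3000 replicates per rho, sex as covariate, dropout split evenly before and after T2) gave these ratios at T2/T3: 1.53/1.46, 1.25/1.23 and 1.15/1.12. The mean error of either estimator was at most 0.012 SD.

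**6. Single-visit power at d = 0.48, 25 per arm (noncentral t, change to adjusted).** The plan does not say which SD standardizes d, so both scales are shown.

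- rho 0.3: 29% to 41% if d is in raw-SD units; 38% to 54% if in change-SD units
- rho 0.7: 57% to 64%, or 38% to 44%

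These concern one visit and are not the three-measure interaction test of step 1.

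**The case against.** **The model is inferred.** No equation is given, RM ANCOVA is mentioned as an option, and a GEE of T2 and T3 with T1 as covariate is not ruled out. That is true. But the text names only sex, prefers GEE, frames the contrasts as change from pre-treatment and counts three repeated measures. If T1 adjustment is intended, one sentence would settle it.

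**Equal SDs are assumed.** The documents do not supply the SDs, and the eligibility criteria (section 2.2) select children whose parents report poor sleep or its effects, so the spread at T1 may differ. Writing k for the T1 SD divided by the follow-up SD, the ratio is (1 + k² − 2·k·rho)/(1−rho²). At k = 0.8 it is 1.27 for rho 0.3 and 1.02 for rho 0.7. At k = 0.7 with rho 0.7 it is 1.00, so there is no loss. At k = 1.2 with rho 0.3 it is 1.89. This stands: 18% is not a floor and 54% is not a ceiling. In large samples, however, the adjusted contrast is never the less precise of the two.

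**T1 may be missing.** The skin-irritation text in section 10.1 lets a child who cannot tolerate the watch remove it, so some baseline actigraphy may be absent. This is fair, and the fix needs a rule for it. The attrition figures also use all available data, whereas the plan intends multiple imputation.

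**It is a pilot focused on feasibility, and nothing is biased.** Both are true, and they keep this from being a question of validity. Effect-size estimation is nevertheless a stated purpose, and the plan already cites power as a reason for its choice of method.

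**Conclusion.** The point holds as a loss of precision, not of validity. On the natural reading, the plan's contrast has 2/(1+rho) times the variance of a T1-adjusted one: 54% more at its own correlation of 0.3 (about 50% more once the slope is estimated at 25 per arm), falling to 18% (about 14%) at 0.7. The figures are per visit. They rest on equal SDs at T1 and follow-up and on the efficacy contrast being change from T1; only the 0.3 comes from the plan. The gain is substantial if the plan's correlation is right and modest if the true one is much higher. Since it costs almost nothing, it should be taken.

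**What to change.** Write the model into the Data Analysis Plan, in one of two forms:

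- Analyse T2 and T3 as the outcome vector, with the T1 value of the same outcome, sex, visit, arm and arm-by-visit as terms. GEE can be kept.
- Keep T1 in the outcome vector and fit a constrained longitudinal model with one T1 mean common to both arms. In a simulated complete-data GEE at rho 0.3 this recovered most of the gain (variance ratio 1.46).

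Report the adjusted between-arm difference at each visit with its 95% CI. State which SD standardizes any effect size, and report the observed SDs and the correlation of T1 with each follow-up visit, which the definitive trial's sample-size calculation will need. Add a rule for a missing T1 value: either include T1 in the imputation model already planned, or use the common-baseline form, which can retain children without T1.

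The cost is a few sentences, a change to the code and about one degree of freedom per outcome. T1 is already part of the assessment schedule, so no new data are needed. Fixing the model in advance also removes a later choice between change-score and adjusted results, which can differ at this sample size.
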